### **2.1.3 Durvalumab**

Durvalumab is a human monoclonal antibody (mAb) of the immunoglobulin G (IgG) 1 kappa subclass that blocks the interaction of PD-L1 (but not programmed cell death ligand-2) with PD-1 on T cells and CD80 (B7.1) on immune cells (IC). It is being developed by AstraZeneca/MedImmune for use in the treatment of cancer. (MedImmune is a wholly owned subsidiary of AstraZeneca; AstraZeneca/MedImmune will be referred to as AstraZeneca throughout this document.) The proposed mechanism of action (MOA) for durvalumab is interference in the interaction of PD-L1 with PD-1 and CD80 (B7.1). Blockade of PD-L1/PD-1 and PD-L1/CD80 interactions releases the inhibition of immune responses, including those that may result in tumor elimination. In vitro studies demonstrate that durvalumab antagonizes the inhibitory effect of PD-L1 on primary human T cells resulting in the restored proliferation of IFN- $\gamma$  (Stewart et al 2015). In vivo studies have shown that durvalumab inhibits tumor

growth in xenograft models via a T-cell-dependent mechanism (Stewart et al 2015). Based on these data, durvalumab is expected to stimulate the patient's antitumor immune response by binding to PD-L1 and shifting the balance toward an antitumor response. Durvalumab has been engineered to reduce antibody-dependent cellular cytotoxicity and complement-dependent cytotoxicity.

To date, durvalumab has been given to more than 6000 patients as part of ongoing studies either as monotherapy or in combination with other anticancer agents. Details on the safety profile of durvalumab monotherapy are summarized in Section 7.5 Refer to the current durvalumab IB for a complete summary of pre-clinical and clinical information including safety, efficacy, and pharmacokinetics (PK).

#### **2.1.4 Durvalumab in combination with chemotherapy**

Nonclinical and clinical studies have indicated that blockade of immune checkpoints (PD-1/PD-L1) can have a positive effect on antitumor immunity. Patients with SCLC may be particularly susceptible to these immunotherapies given the high mutational burden of this disease (Salgia and Skarin 1998). The use of combination chemotherapy is a mainstay of oncology therapy. The goal of combination chemotherapy is to utilize agents that affect cancer cells by different mechanisms, thus reducing the risk of developing resistance. Current investigations are now adding immunotherapeutics to chemotherapeutics to broaden antitumor responses.

Checkpoint inhibitors have been tested in SCLC, either used alone or in combination with chemotherapy. The IMpower133 study was presented at the World Congress on Lung Cancer (Horn et al 2018). IMpower133 was a randomized placebo-controlled phase III study, comparing atezolizumab + etoposide/carboplatin (EC) with placebo + EC in first line treatment of ES-SCLC. The study demonstrated a statistically significant improvement in OS with the combination of atezolizumab + etoposide/carboplatin compared to placebo + EC. Meanwhile, the CASPIAN study which was presented at the World Congress on Lung Cancer (Paz-Ares et al 2019) demonstrated a statistically significant improvement in OS of durvalumab plus etoposide/platinum (EP) compared to etoposide/platinum (EP) in first-line SCLC as well. CASPIAN was a randomised, open-label, phase 3 trial, to assess durvalumab, with or without tremelimumab, in combination with etoposide plus either cisplatin or carboplatin (EP) in treatment-naïve patients with ES-SCLC. CASPIAN met its primary endpoint of overall survival for durvalumab plus EP versus EP at the planned interim analysis, with a hazard ratio of 0.73 (95% CI 0.59–0.91;  $p=0.0047$ ); median overall survival was 13.0 months (95% CI 11.5–14.8) in the durvalumab plus EP group versus 10.3 months (9.3–11.2) in the EP group. Any-cause adverse events of grade 3 or 4 occurred in 163 (62%) of 265 treated patients in the durvalumab plus EP group and 166 (62%) of 266 in the EP group; adverse events leading to death occurred in 13 (5%) and 15 (6%) patients in the two groups, respectively. Immune-mediated adverse events (imAEs) were reported in 52 (20%) of 265 patients treated with durvalumab plus EP and seven (3%) of 266 patients treated with EP alone. Most of these events were grade 1 or 2; grade 3 or 4 imAEs occurred in 12 patients (5%) in the durvalumab plus EP group and one patient (<1%) in the EP group. Deaths due to imAEs occurred in one (<1%) patient in each group; causes of death were hepatotoxicity in

the durvalumab plus EP group and pneumonitis in the EP group. The most common imAEs were hypothyroid events (occurring in 24 [9%] patients in the durvalumab plus EP group and two [1%] patients in the EP group) and hyperthyroid events (occurring in 14 [5%] and none in the two groups, respectively), which were all grade 1 or 2 in severity.

### **2.1.5 Rationale for conducting this study**

ES-SCLC is an aggressive malignancy and the prognosis remains poor despite favorable initial response to platinum-based chemotherapy, which has been the standard treatment for over 3 decades. Recently, immunotherapy targeting the programmed cell death-1 (PD-1) and programmed cell death ligand-1 (PD-L1) pathway has demonstrated clinical activity for patients with ES-SCLC, including as first-line treatment. While the CASPIAN study demonstrated improved OS with the addition of durvalumab to carboplatin or cisplatin plus etoposide (Paz-Ares 2019), there remains unmet needs for improved treatments in first line ES-SCLC in China, particularly more safety data for patients who would not have been included in CASPIAN study, including the ECOG PS=2 population and for those patients for whom flexible number of chemotherapy cycles is important in treatment decision making.

## **2.2 Benefit/risk assessment**

The following sections include summaries of the potential benefits and risks associated with durvalumab prior to the overall benefit-risk assessment. More detailed information about the known and expected benefits and risks and reasonably expected adverse events of durvalumab may be found in the Investigator's Brochure.

### **2.2.1 Potential Benefits**

#### **2.2.1.1 Durvalumab**

The majority of the safety and efficacy data currently available for durvalumab monotherapy are based on the first-in-human, single-agent study (Study 1108) in patients with advanced solid tumors. Overall, as of 7 May 2015, 456 of 694 patients treated with [REDACTED]

#### **2.2.1.2 Durvalumab + chemotherapy**

Studies evaluating agents targeting PD-L1 or CTLA-4 in combination with chemotherapy have yielded encouraging results.

The Phase III CASPIAN study demonstrated a statistically significant improvement in OS for durvalumab plus etoposide/platinum (EP) compared to EP alone as first-line treatment for ES-SCLC at a pre-planned interim analysis with a hazard ratio of 0.73 (95% CI 0.59–0.91;  $p=0.0047$ ). The median overall survival was 13.0 months (95% CI 11.5–14.8) in the durvalumab plus EP group versus 10.3 months (95% CI 9.3–11.2) in the EP alone group. The OS improvement with durvalumab plus EP was demonstrated across all pre-specified

subgroups. The secondary endpoint of progression free survival (PFS) was also improved with durvalumab plus EP versus EP (PFS HR: 0.78 [95% CI, 0.645–0.936]; median PFS, 5.1 vs. 5.4 months); the 12-month PFS rate was 17.5% vs. 4.7%, respectively. Durvalumab plus EP showed a 10% improvement in confirmed objective response rate (ORR) compared to EP; 67.9% vs. 57.6%, respectively. The treatment effects of durvalumab + EP were sustained over time compared to EP alone, as supported by the estimates of the 18 month OS rate, as well as the 12-month OS, PFS, and Duration of Response rates: 53.7% vs 39.8% of patients were alive at 12 months; an estimated 33.9% vs 24.7% of patients were alive at 18 months; and the 12-month PFS rate was 17.5% vs 4.7%, across the two groups, respectively.

## **2.2.2 Overall Risks**

Monoclonal antibodies directed against immune checkpoint proteins, such as programmed cell death ligand 1 (PD-L1) as well as those directed against programmed cell death-1 (PD-1), aim to boost endogenous immune responses directed against tumor cells. By stimulating the immune system however, there is the potential for adverse effects on other tissues.

Most adverse drug reactions seen with the immune checkpoint inhibitor class of agents are thought to be due to the effects of inflammatory cells on specific tissues. These risks are generally events with a potential inflammatory or immune-mediated mechanism and which may require more frequent monitoring and/or unique interventions such as immunosuppressants and/or endocrine therapy. These immune-mediated effects can occur in nearly any organ system, and are most commonly seen as gastrointestinal AEs such as colitis and diarrhea, pneumonitis/interstitial lung disease (ILD), hepatic AEs such as hepatitis and liver enzyme elevations, skin events such as rash and dermatitis, and endocrinopathies including hypo- and hyper-thyroidism.

### **2.2.2.1 Durvalumab**

Risks with durvalumab include, but are not limited to, diarrhea/colitis, pneumonitis/ILD, endocrinopathies (ie, events of hypophysitis/hypopituitarism, adrenal insufficiency, hyper- and hypo-thyroidism, type I diabetes mellitus and diabetes insipidus), hepatitis/increases in transaminases, nephritis/increases in creatinine, , rash/dermatitis, myocarditis, myositis/polymyositis, infusion-related reactions, hypersensitivity reactions, pancreatitis, serious infections, and other rare or less frequent inflammatory events including neuromuscular toxicities (e.g. Guillain Barre syndrome, myasthenia gravis).

For information on all identified and potential risks with durvalumab, please always refer to the current version of the durvalumab IB.

In monotherapy clinical studies, AEs at an incidence of  $\geq 20\%$  include events such as fatigue, cough, decreased appetite, dyspnea and nausea. Approximately 10% of patients discontinued the drug due to an AE. Please see the current version of the IB for a detailed summary of the monotherapy data including AEs, SAEs, and CTC Grade 3 to 5 events reported across the durvalumab program.

The majority of treatment-related AEs were manageable, with dose delays, symptomatic treatment, and in the case of events suspected to have an immune basis, the use of established treatment guidelines for immune-mediated toxicity (see Section 7.9.1).

A detailed summary of durvalumab monotherapy AE data can be found in the current version of the durvalumab IB.

### **2.2.2.2 Durvalumab + chemotherapy**

The safety and tolerability of the combination of durvalumab plus chemotherapy was evaluated in two studies evaluating different chemotherapy regimens in patients with solid tumors: AZ study D419SC00001 and CCTG study NCT02537418. In general, the combination of durvalumab plus tremelimumab with chemotherapy appeared tolerable and manageable. On all dose levels, dose delays of durvalumab were mostly for administrative reasons/patient request and neutropenia related to chemotherapy.

In the randomized phase III CASPIAN study, durvalumab + EP was tolerable and manageable as first line treatment for ES-SCLC. The safety profile was consistent with the known profile of all the agents and no new safety signals were identified. In summary, any-cause adverse events of any grade were reported in 98.1% vs 97.0% of patients in the durvalumab +EP and EP alone groups, respectively. Rates of grade 3 or 4 occurred in 163 (62%) of 265 treated patients in the durvalumab plus EP group and 166 (62%) of 266 in the EP group; serious adverse events (SAEs) occurred in 30.9% of patients treated in the durvalumab plus EP group and 36.1% of patients treated in the EP group; adverse events leading to death occurred in 13 (5%) and 15 (6%) patients. Adverse events of any cause leading to discontinuation of study treatment occurred in 9.4% of the patients treated in both the durvalumab + EP and the EP alone groups. Immune-mediated adverse events (imAEs) were reported in 52 (20%) of 265 patients treated with durvalumab plus EP and seven (3%) of 266 patients treated with EP, Most of these events were grade 1 or 2 and were endocrine related; grade 3 or 4 imAEs occurred in 12 patients (5%) in the durvalumab plus EP group and one patient (<1%) in the EP group.

External clinical data also supports these findings. In the randomized Phase III study IMpower133 demonstrated that the safety profile of atezolizumab plus EC was consistent with the previously reported safety profile of the individual agents, with no new findings observed.

### **2.2.3 Overall benefit-risk assessment**

There remains a significant unmet medical need for additional treatment options for patients with ES-SCLC. Four or six cycles of platinum-based chemotherapy has been considered the standard treatment regimens for the last several decades; however, OS remains poor with a 2-year survival rate of 5% despite favorable initial responses. The vast majority of ES-SCLC patients will relapse with a median time to progression of 4 to 6 months and a median OS of 7 to 11 months. The poor prognosis reflects the limited treatment options available, highlighting the need for the development of newer therapeutic options.

Recently, immune checkpoint inhibitors targeting the programmed cell death-1 (PD-1) and programmed cell death ligand-1 (PD-L1) pathway have demonstrated clinical activity across

multiple lines of therapy for patients with ES-SCLC.

In the Phase III CASPIAN study, durvalumab + EP demonstrated a statistically significant and clinically meaningful improvement in OS versus EP alone, reducing the risk of death by 27% for this challenging-to-treat disease. Importantly, these clinical benefits were observed in the context of a clinically relevant control arm that permitted up to 6 cycles of EP (compared with 4 cycles in the durvalumab + EP arm) and PCI at the investigator's discretion. Median OS was 13.0 versus 10.3 months for durvalumab plus EP versus EP alone and the OS benefit was observed across all clinically relevant patient subgroups. Consistent with the results for OS, PFS was also improved for durvalumab plus EP versus EP, as was confirmed ORR, with an incremental improvement of 10.3% between arms (67.9% vs. 57.6%). OS benefit was durable for durvalumab plus EP compared with EP, as evidenced by the tail of the Kaplan-Meier curve; in the durvalumab plus EP arm, an estimated 53.7% of patients were alive at 12 months and 33.9% of patients were alive at 18 months, compared to an estimated 39.8% and 24.7% of patients on the EP alone arm, respectively, at these landmarks. Sustained clinical benefit was also observed across PFS and tumor response with durvalumab plus EP versus EP, with 12-month PFS rates of 17.5% versus 4.7%, and 22.7% versus 6.3% of patients remaining in response at 12 months, respectively. These gains in long term clinical benefit are meaningful to patients with this recalcitrant disease.

[REDACTED]

[REDACTED]

[REDACTED]

### 3 OBJECTIVES AND ENDPOINTS

All objectives will be evaluated for all patients, unless otherwise indicated.

| Primary objective:  | Endpoint/variable:                             |
|--|---|
| To assess the safety and tolerability of durvalumab + EP in patients with performance status 0-2 | Incidence of Grade $\geq 3$ AEs
Incidence of imAEs |

AE Adverse event; EP Etoposide and platinum-based chemotherapy; imAE Immune-mediated adverse event.

| Secondary objective:   | Endpoint/variable:  |
|---|--|
| To assess the efficacy of durvalumab + EP in patients with performance status 0-2 | PFS, APF12, ORR, DoR using site Investigator assessment and OS, OS12     |
| To further assess the safety and tolerability profile of durvalumab + EP          | Incidence of AEs, SAEs, AESIs, AE resulting in treatment discontinuation |

AESIs adverse event of special interest; DoR Duration of Response; EP Etoposide and platinum-based chemotherapy; ORR Objective response rate; OS Overall survival; OS12 Overall survival at 12 months after first dose of study treatment; PFS Progression free survival; APF12 Proportion of patients alive and progression free at 12 months after first dose of study treatment.

## 4 STUDY POPULATION

Each patient must meet all of the inclusion criteria (Section 4.1) and none of the exclusion criteria (Section 4.2) for this study at the screening visits. Under no circumstances will there be exceptions to this rule.

### 4.1 Inclusion criteria

For inclusion in the study, patients should fulfill the following criteria:

1. Male or female  $\geq 18$  years at the time of Screening.
2. Written informed consent obtained from the patient/legal representative prior to performing any protocol-related procedures, including screening evaluations.
3. Histologically or cytologically documented extensive stage SCLC (stage IV [T any, N any, M1 a/b], or with T3-4 due to multiple lung nodules that are too extensive or have tumor/nodal volume that is too large to be encompassed in a tolerable radiation plan, according to American Joint Committee on Cancer Stage 8th edition).
  - Brain metastases; must be asymptomatic or treated and stable off steroids and anti-convulsants for at least 1 month prior to study treatment. Patients with suspected brain metastases at screening should have a CT/MRI of the brain prior to study entry.
4. Patients must be considered suitable to receive a platinum-based chemotherapy regimen as 1st line treatment for the ES-SCLC. Chemotherapy must contain either cisplatin or carboplatin in combination with etoposide.
5. Life expectancy  $\geq 12$  weeks at Day 1.
6. World Health Organization (WHO)/Eastern Cooperative Oncology Group (ECOG) Performance Status of 0 to 2 at enrollment.

- Note: Patients with PS2 will be limited to a maximum of 20% of the total study population; once this limit is met, additional enrolled patients must have PS 0-1.
7. Body weight >30 kg.
  8. At least 1 lesion, not previously irradiated, that can be accurately measured at baseline as  $\geq 10$  mm in the longest diameter (except lymph nodes which must have a short axis  $\geq 15$  mm) with computed tomography (CT) or magnetic resonance imaging (MRI) and that is suitable for accurate repeated measurements as per RECIST 1.1 guidelines.
  9. Baseline CT/MRI results of the chest and abdomen (including liver and adrenal glands) within 28 days prior to the treatment initiation.
  10. No prior exposure to immune-mediated therapy including, but not limited to, other anti-CTLA-4, anti-PD-1, anti-PD-L1, and anti-programmed cell death ligand 2 (anti-PD-L2) antibodies, excluding therapeutic anticancer vaccines.
  11. Adequate organ and marrow function as defined below (test can be repeated once if necessary):
    - Hemoglobin  $\geq 9.0$  g/dL.
    - Absolute neutrophil count  $\geq 1.5 \times 10^9/L$  (use of granulocyte colony-stimulating factor is not permitted within 7 days before testing).
    - Platelet count  $\geq 100 \times 10^9/L$ .
    - Serum bilirubin  $\leq 1.5 \times$  the upper limit of normal (ULN).
    - In patients without hepatic metastasis: ALT and AST  $\leq 2.5 \times$  ULN.
    - In patients with hepatic metastases, ALT and AST  $\leq 5 \times$  ULN.
    - Measured or calculated creatinine clearance:  $>60$  mL/min for patients planned to be treated with cisplatin and  $>40$  mL/min for patients planned to be treated with carboplatin
  12. Evidence of post-menopausal status or negative urinary or serum pregnancy test for female pre-menopausal patients. Women will be considered post-menopausal if they have been amenorrheic for 12 months without an alternative medical cause.

The following age-specific requirements apply:

- Women <50 years of age would be considered post-menopausal if they have been amenorrheic for 12 months or more following cessation of exogenous hormonal treatments and if they have luteinizing hormone and follicle stimulating hormone levels in the post-menopausal range for the institution or underwent surgical sterilization (bilateral oophorectomy or hysterectomy).
- Women  $\geq 50$  years of age would be considered post-menopausal if they have been amenorrheic for 12 months or more following cessation of all exogenous hormonal treatments, had radiation-induced menopause with last menses  $>1$  year ago, had chemotherapy-induced menopause with last menses  $>1$  year ago, or underwent surgical sterilization (bilateral oophorectomy, bilateral salpingectomy or hysterectomy).

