### **Target patient population**

Adult patients (aged  $\geq 18$  years) with histologically or cytologically documented extensive stage SCLC (stage IV [T any, N any, M1 a/b/c], or with T3-4 due to multiple lung nodules that are too extensive or have tumor/nodal volume that is too large to be encompassed in a tolerable radiation plan according to American Joint Committee on Cancer Stage (8th edition). Patients must have World Health Organization/Eastern Cooperative Oncology Group performance status of 0-2; patients with PS2 will be limited to 20% of the total study population.

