### **4.4 Procedures for handling incorrectly enrolled**

Patients who fail to meet the eligibility criteria should not, under any circumstances, be enrolled or receive study medication. There can be no exceptions to this rule. Patients who are enrolled but found to not meet all the eligibility criteria must not be initiated on treatment and must be withdrawn from the study as a screen failure.

When a patient does not meet all the eligibility criteria but is incorrectly started on treatment, the investigator should inform the AstraZeneca Study Physician immediately, and the Study Physician and the investigator should discuss whether to continue or discontinue the patient from treatment. The Study Physician must ensure that all decisions are appropriately documented.

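### Criterion 3 lists stage IV as M1 a/b and the synopsis lists M1 a/b/c, so an M1c patient qualifying only through stage IV is in the target population but ineligible

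*Protocol*

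**What the plan says.** The population is described in two places. The synopsis, under Target patient population, gives extensive-stage disease as "stage IV [T any, N any, M1 a/b/c], or with T3-4 due to multiple lung nodules", with staging "according to American Joint Committee on Cancer Stage (8th edition". Criterion 3 in Section 4.1 uses almost the same sentence, "stage IV [T any, N any, M1 a/b], or with T3-4 due to multiple lung nodules", with staging "according to American Joint Committee on Cancer Stage 8th edition".

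Section 4.1 is binding. Section 4 requires every inclusion criterion to be met and no exclusion criterion to apply, and adds: "Under no circumstances will there be exceptions to this rule". Section 4.4 says: "Patients who fail to meet the eligibility criteria should not, under any circumstances, be enrolled or receive study medication". It sends a patient found ineligible before treatment out of the study as a screen failure, and a patient already started on treatment to a discussion between the investigator and the Study Physician. Section 4.3 also bars treatment unless all criteria are met.

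Section 4.1 also contains text that presupposes distant disease: "Brain metastases; must be asymptomatic or treated and stable off steroids", and a separate liver-enzyme limit that begins "In patients with hepatic metastases, ALT and AST".

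**The concern.** A criterion that allows no exceptions should describe the same patients as the target population. Here it does not. For an M1c patient whose eligibility rests on the stage IV branch, the synopsis says the patient is intended for the study and Section 4.1 says the patient may not enter. A site that follows Section 4.1 records a screen failure. A site that follows the synopsis enrols the patient and creates an eligibility deviation.

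The study has a single arm, and its primary result is the incidence of Grade 3 or higher adverse events and of immune-mediated adverse events. With no comparator, the meaning of those percentages depends on who was eligible. At stake are three things: which patients may enter, which treated patients count as eligibility deviations, and which population the reported incidences describe.

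**Working it through.** No arithmetic applies, and the plan gives no figure to reproduce. The check compares the two texts.

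**1. The two definitions side by side**

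| Element | Synopsis, Target patient population | Section 4.1, criterion 3 |
|---|---|---|
| Disease | extensive-stage SCLC, by histology or cytology | same |
| Stage IV branch: T and N | any T, any N | same |
| Stage IV branch: M | M1 a, b, c | M1 a, b |
| Alternative branch | T3-4 with disease too extensive for a tolerable radiation plan | same |
| Staging edition | AJCC 8th | AJCC 8th |

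The only substantive difference is that M1c is missing from criterion 3.

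**2. Is this superseded or damaged text?** No. Both statements are in the current version 2.0 text and nothing is redacted at either place. For Section 4.1, the version history names criteria 8 and 11 and does not mention criterion 3. In any case the conflict is between two current statements, not between current text and the log.

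**3. Which patients are caught?** Criterion 3 has two branches joined by an or. The stage IV branch lists M categories; the T3-4 branch states none.
- M1a or M1b: admitted by both texts.
- M1c, also meeting the T3-4 branch: arguably admitted by both texts.
- M1c, not meeting the T3-4 branch: in the synopsis population, ineligible under Section 4.1.

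The contradiction is confined to the third group.

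**4. Does anything else settle the intent?** Section 4.2 names no M category, and no rationale for a narrower range appears. The title and synopsis speak of extensive-stage disease generally. Section 4.1 sets conditions for brain metastases and a liver-enzyme limit for hepatic metastases, and exclusion criterion 6 mentions palliative radiation for bone metastasis. All this points to an omission, but it does not prove one: the protocol does not define M1a, M1b or M1c, so these provisions could still serve patients within the shorter list.

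**5. Can a site resolve it by judgement?** No. The no-exceptions rule in Section 4 and the bar in Section 4.4 leave no latitude. The synopsis itself refers enrolment to the inclusion and exclusion criteria, so Section 4.1 governs in practice.

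**The case against.** The strongest reply is that this is a dropped letter that sites will read through. The leading term of criterion 3 is extensive-stage disease, the bracket only expands stage IV, and the surrounding provisions expect distant metastases. The study is also descriptive: it has no hypothesis test and no formal sample size calculation. Under Section 9.3 every treated patient enters the safety analysis set, which also serves for efficacy, so an M1c patient treated in breach of criterion 3 stays in the analysis. No estimator, interval method or endpoint definition changes.

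Much of this stands. The context does favour an omission, and the analysis rules are untouched. It does not remove the problem, because the text with the dropped letter is the one that decides entry, and the protocol forbids sites to depart from it. Retaining every treated patient does nothing for those turned away at screening, nor does it settle whether a treated M1c patient is a deviation.

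A reader might infer more than the documents support:
- That all M1c patients are excluded. The T3-4 branch carries no M restriction, so that is too strong.
- That a cohort limited to M1a/b would be healthier, or that case mix and event rates differ between sites. The protocol neither defines the M categories nor links them to outcome, and it does not show that sites have read the criterion differently.
- That the screening burden rises by a calculable factor. That needs the M1c share, which the documents do not give, and it would also have to allow for the T3-4 branch.

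**Conclusion.** The point holds as an internal inconsistency in a binding eligibility criterion. Under one staging edition, the synopsis admits M1 a/b/c and criterion 3 admits M1 a/b. An M1c patient who qualifies only through stage IV therefore belongs to the target population and is ineligible under Section 4.1. The size is limited to that group, and its share of patients cannot be stated from the documents. No bias in the primary incidences is shown; what is unclear is who may be enrolled, who is a deviation and whom the incidences describe. The conclusion assumes only that Section 4.1 is applied as written, which Sections 4 and 4.4 require. It should be corrected because it governs enrolment decisions and the correction costs almost nothing.

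**What to change.** Put one list of M categories in both places. If the synopsis population is the intended one, criterion 3 should read M1 a/b/c. If the shorter list was deliberate, the synopsis should match it and the protocol should give the reason. Send sites a short clarification. Search the screen-failure and deviation logs for patients turned away or classed as deviations because of M category, and report enrolment by M category so that readers can see whom the results cover.

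The text change is a single letter in one section or the other, plus a sentence of rationale if the list is narrowed. Add the usual approval steps for an amendment, one site memo and a log review. The analyses do not change.
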